17.1 Format of the Case Report Forms

In this study, the electronic CRF (eCRF) and electronic data capture (EDC) system will be used. The investigator will review its content and attach the digital signature. The study site will provide the sponsor with electronic data on the results of general laboratory tests (except for the result of coagulation test and hCG). The drug concentration measurement site will provide the sponsor with electronic data on the result of drug concentration measurement.

17.2 Data to Be Directly Recorded in the CRF and Handled as the Source Data

The following data recorded in the CRF will be handled as the source data. However, when this information is recorded in a medical record, the medical record will be handled as the source data.

- (1) Purpose(s) of the use of concomitant medication(s)
- (2) AEs (seriousness, severity, outcome, date and time of outcome, relationship to the investigational product, reason[s] for determination of the relationship to the investigational product)
- (3) Date and reason of discontinuation, AE leading to discontinuation, courses and follow-up results after discontinuation
- (4) Comments from the investigator (or subinvestigator)

For the results of general laboratory test and drug concentration measurement, a test slip and a report from the drug concentration measurement site will be used as a source data, respectively. If any content is changed from the above, the sponsor and the investigator will specify the changes in writing, prior to the start of the study.

17.3 Notes for Data Entry in the CRFs

The investigator (or subinvestigator) or study collaborator will prepare CRFs according to the following specifications. CRFs will be prepared according to the "Guide to Changing or Correcting Case Reports" provided separately by the sponsor.

- (1) Prior to data entry to the CRFs, the sponsor will provide the investigator (subinvestigator) and study collaborator with user IDs and passwords for user management. The investigator (subinvestigator) and study collaborator will maintain the assigned user IDs and passwords themselves, and will not share them with any other persons. Data will be entered by the investigator (or subinvestigator) or by a study collaborator who is authorized for data entry.
- (2) CRFs will be created for subjects receiving the investigational product.
- (3) The investigator can enter data in all fields of the CRF. The subinvestigator is allowed to enter data in all fields of the CRF, except for the digital signature. A study collaborator is allowed to transcribe data from the source data (e.g., medical records) to CRFs, for data that requires no medical judgment.
- (4) When changing or correcting a recorded CRF, the reason for the change or correction will be recorded in the form of electronic data.
- (5) The investigator will confirm that the CRF is accurate and complete and that the audit trail and digital signature can be confirmed. After the confirmation, the investigator will enter the digital signature on the CRF in the EDC system.
- (6) The investigator will maintain storage media (e.g., CD-R) that contains a copy of the CRFs (that are checked by the investigator and stored in PDF files). The eCRFs will be accessible

Confidential

(via access rights in the EDC system) after the attachment of the digital signature, until the receipt of storage media (e.g., CD-R) from the sponsor that serves as a substitute copy.

(7) If there are any discrepancies between the data entered in the CRF and the source data, the investigator will create a separate report detailing the reasons for the discrepancy, submit it to the sponsor, and retain a copy.

17.4 Time Points to Submit CRFs

The investigator (or subinvestigator) will promptly complete eCRF entry after the specified tests and observations.

18. Direct Access to the Source Data

The investigator and the head of the study site will allow direct access to all study-related data by the sponsor for monitoring and auditing, or by the IRB or regulatory authorities for inspections.

19. Quality Control and Quality Assurance of the Study

The sponsor shall conduct the “quality control and quality assurance of the study” to maintain the quality and reliability of the study, according to the GCP standard operating procedure of Mitsubishi Tanabe Pharma Corporation. The study site and the investigator shall cooperate with the sponsor for the quality control and quality assurance of the study.

For the quality control of the study, the monitor shall confirm that the study is being performed in compliance with the study-related procedures of the study site, latest protocol, and GCP through appropriate direct access to the source data. The monitor will also review that the CRFs provided by the investigator (or subinvestigator) are accurate and complete, and confirm that they are verifiable with study-related records such as the source data.

In order to assure implementation of the study in compliance with the protocol and GCP, the auditor shall conduct audits in accordance with the GCP standard operating procedure, in order to confirm that quality control is properly performed.

20. Ethics

20.1 Ethical Conduct of the Study

This study shall be conducted in accordance with ethical principles that have their origin in the Declaration of Helsinki, the Law on Securing Quality, Efficacy and Safety of Products Including Pharmaceuticals and Medical Devices, GCP, and the protocol.

20.2 Institutional Review Board

The IRB shall review the study from ethical, scientific, medical, and pharmaceutical perspectives to determine the implementation and continuation of the study based on the investigator's brochure, protocol, informed consent form, and written information.

20.3 Protection of Subject Confidentiality

When enrolling subjects and filling in the CRFs, the investigator will specify each subject using a subject ID code. In addition, subject confidentiality shall be protected at the time of direct access to the source data, publication to medical journals, and data submission to the regulatory authorities.

Confidential

21. Retention of Records

(1) Records to be retained at the study site

The record storage manager assigned by the head of the study site will store records related to the study at the study site until date 1) or 2) below, whichever comes later. However, when the sponsor deems it necessary to retain these records for a longer period, the storage period and method of storage shall be decided upon discussion with the sponsor.

If the sponsor decides not to attach the clinical study results collected from the study to the application for marketing approval, the sponsor will report this decision and the reason to the head of the study site in writing.

In addition, when the marketing approval of the investigational product is obtained, or when the marketing approval is not obtained and development is terminated, the sponsor will report these matters to the head of the study site in writing.

- 1) The date of marketing approval of the investigational product (date of approval for partial changes for approval for additional indications) (When development is terminated, or when a notification has been received indicating that the study results will not be attached to the application, this will be 25 years from the date of receiving the notification.)
- 2) Twenty-five years from the date of study termination or completion

(2) Records to be retained by the sponsor

The sponsor will store records relating to the study at the sponsor until date 1) or 2) below, whichever comes later.

- 1) Twenty-five years from the date of marketing approval of the investigational product (date of approval for partial changes for approval for additional indications) or date of completion of reexamination (When development is terminated, this will be 25 years from the date of the decision for development termination.)
- 2) Twenty-five years from the date of study termination or completion

22. Payment to the Subjects

Payment to the subjects and the study site will be made according to the contract or agreement between the study site and the sponsor.

23. Compensation for Health Hazards and Insurance

23.1 Compensation for Health Hazards

If any health hazards to the subjects are caused by this study, the sponsor assures appropriate compensation for such health hazards, according to the standards specified by the sponsor, except in cases where it is determined that the health hazard is not related to the study. (This compensation includes medical expenses, medical allowances, and compensation money.) In such cases, the sponsor will not impose a burden on the subjects regarding proof of the relationship to the study treatment.

8.3.5. Physical Examinations	23
8.4. Pharmacokinetics Evaluation.....	23
8.4.1. Concentrations and Pharmacokinetic Parameters for unchanged edaravone, sulfate conjugate, and glucuronide conjugate	24
8.4.2. Analysis of Food Effect.....	24
9. DATA PRESENTATION CONVENTIONS	25
9.1. Number of Digits to Report	25
9.2. Treatments to Report.....	26
9.3. Analysis Visits to Report	26
10. CHANGE FROM THE PROTOCOL	27
11. SOFTWARE.....	27
12. REFERENCES	27

ABBREVIATIONS

Abbreviations	Definitions
AE	adverse event
ALT	alanine transaminase
ALP	alkaline phosphatase
AST	aspartate transaminase
ATC	anatomical therapeutic chemical
BLQ	below limit of quantification
BMI	body mass index
CI	confidence interval
CV	coefficient of variation
DP	decimal places
DRM	data review meeting
ECG	electrocardiogram
MedDRA	medical dictionary for regulatory activities
PK	pharmacokinetics
PT	preferred term
SAP	statistical analysis plan
SAE	serious adverse event
SAF	safety population
SD	standard deviation
SOC	system organ class
WHO	World Health Organization

LIST OF PK PARAMETERS

Parameters	Definitions
AUC_{0-24}	Area under the plasma concentration-time curve from zero up to 24 hour
AUC_{0-t}	Area under the plasma concentration-time curve from zero up to the last quantifiable concentration time point
$AUC_{0-\infty}$	Area under the plasma concentration-time curve from zero up to infinity with extrapolation of the terminal phase
$AUC\%_{ex}$	Area under the (plasma) concentration-time curve extrapolated from the last quantifiable concentration time point to infinity in % of the total $AUC_{0-\infty}$
Ae_{0-24}	Cumulative urinary excretion amount of drug from zero to 24 hour
Ae_{0-48}	Cumulative urinary excretion amount of drug from zero to 48 hour
C_{max}	Maximum plasma concentration after administration
C_{last}	Last quantifiable concentration
CL/F	Apparent total clearance
CL_r	Renal clearance
Kel	Elimination rate constant from the central compartment
$LLOQ$	Lower limit of quantification
LOQ	Limit of quantification
MRT	Mean residence time
NC	Not calculated
$t_{1/2}$	Terminal elimination half-life in plasma concentration-time course
V_{ss}/F	Apparent volume of distribution at steady state
V_z/F	Apparent volume of distribution during terminal phase
$Ae\%$	Urinary excretion ratio of drug

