Appendix 1 Pregnancy Report

Attachments

- Attachment 1 Administrative Structure
- Attachment 2 ENSURE LIQUID® Package Insert

Confidential

List of Abbreviations

Abbreviations	Unabbreviated expressions
ALS	Amyotrophic lateral sclerosis
BCRP	Breast cancer resistance protein
BMI	Body mass index
CYP	Cytochrome P450
EDC	Electronic data capture
GCP	Good clinical practice
HBs	Hepatitis B surface
hCG	Human chorionic gonadotrophin
HCV	Hepatitis C virus
HIV	Human immunodeficiency virus
HR	Heart rate
IC ₅₀	drug concentration associated with 50% inhibition
ICH	International Council for Harmonization of Technical Requirements for Pharmaceuticals for Human Use
MedDRA	Medical Dictionary for Regulatory Activities
OAT	Organic anion transporter
PK	Pharmacokinetic(s)
QTcF	Fridericia's correction of QT
SAE	Serious adverse event
SOD	Superoxide dismutase
TEAE	Treatment-emergent adverse event
UGT	UDP-glucuronyl transferase

Confidential

List of Abbreviations for Pharmacokinetic (PK) Parameters

Abbreviations	Unabbreviated expressions
Ae	Cumulative amount of drug excreted in urine
Ae%	Cumulative percentage of drug excreted in urine
AUC	Area under the plasma concentration-time curve
CL/F	Apparent total clearance
CL _r /F	Apparent renal clearance
C _{max}	Maximum plasma concentration
Kel	Apparent terminal elimination rate constant
MRT	Mean residence time
t _{1/2}	Terminal elimination half-life
t _{max}	Time to reach maximum plasma concentration
V _{ss} /F	Apparent distribution volume at steady state
V _z /F	Apparent distribution volume at elimination phase

Definition of Term

Term	Definition
Day 1	Day 1 is defined as the first day to administer an investigational product.
0 hours	Zero hours (0 h) are defined as the time of administration on the day of dosing an investigational product.
Study period	Period from the time of obtaining the informed consent to the time of completion of the end-of-study assessment or discontinuation assessment (for subjects who have entered into the follow-up period, to the time of completion or termination of the follow-up)

Confidential

Protocol Summary

1 Study Title

Clinical pharmacology study of oral edaravone in healthy adult subjects (food effect study)

2 Study Objectives

Primary objective: To evaluate the effect of food on the pharmacokinetics of oral edaravone in healthy adult subjects.

Secondary objective: To evaluate the pharmacokinetics, safety, and tolerability of oral edaravone.

3 Subjects

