Based on the results of the Phase I clinical pharmacology studies (MT-1186-J01 and MT-1186-J02), time points of blood sampling were set with reference to "Clinical Pharmacokinetic Studies of Pharmaceuticals" [3].

9.2.4.2 Measurement of urine concentrations of unchanged edaravone, sulfate conjugate, and glucuronide conjugate

Urine volume will be measured at voiding and the urine specimen will be processed (see Section 9.2.4.3). The urine is forced to void before administration as well as 24 and 48 hours after administration (46 hours after administration in the conditions C [dosing 4 hours after low-fat meal] and F [dosing 4 hours after light meal]).

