7.1.3.2. Pharmacokinetic Parameters

Below the limit of quantification

For the calculation of PK parameters, actual sampling time (in hours rounded to 3 DPs) relative to dosing should be used. Concentration below the limit of quantification (BLQ) will be imputed with a value of 0. For calculation of AUCs, missing data will be treated as if the respective sample never had been scheduled for the calculation by the linear-linear trapezoidal rule. For Ae, Ae% and CLr, geometric mean and geometric CV% will be calculated only when all the individual Ae, Ae% and CLr is greater than 0 in each sampling time point.

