7.2. Analysis Visit Definitions

(1) Non-PK related

The date of the first dose of investigational product is defined as Day 1.

Excepted for laboratory, baseline will be the last observed value of the parameter of interest prior to the first intake of investigational product by each treatment period (this includes unscheduled visits). For laboratory, baseline will be the last observed value of the parameter of interest prior to the first intake of investigational product (this includes unscheduled visits).

No analysis visit window will not be perfomed for safety evaluation.

(2) PK related

The allowable time window will be the following.

Plasma PK sampling

Nominal Time Point	Window
Predose	Within 60 min before dosing
0.083 h after dosing	Nominal time point \pm 1 min
0.25, 0.5, 0.75, 1, 1.5, 2, 4, 6, 8, 10, 12 h after dosing	Nominal time point \pm 5 min
24, 36 h after dosing	Nominal time point \pm 15 min
48 h* after dosing *Following the dosing 4 hours after meals, blood sampling is conducted 46 h after dosing	
Blood sampling 46 h after dosing	[Period I, II, and III] 45~47 h after dosing and within 60 min before the dosing in the next period [Period IV and V] 45~47 h after dosing
Blood sampling 48 h after dosing	[Period I, II, and III] 47~50 h after dosing and within 60 min before the dosing in the next period [Period IV and V] 47~50 h after dosing

Urine PK sampling

Nominal Time Point	Window
Predose	Within 60 min before dosing
Voluntary Urine	—
Forced micturition at 24 h after dosing	Nominal time point \pm 30 min

Nominal Time Point	Window
Forced micturition at 48* hours post-dose * Forced micturition at 46 h post-dose for subjects dosed 4 h after meals	
Forced micturition at 46 h after dosing	[Periods I, II, and III] 45~47 h after dosing and within 60 min before the dosing in the next period [Periods IV, V] 45~47 h post-dose
Forced micturition at 48 h after dosing	[Periods I, II, and III] 47~50 h after dosing and within 60 min before the dosing in the next period [Periods IV, V] 47~50 h post-dose

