MRT	h	$AUMC_{0-\infty} = \sum_{i=1}^n \frac{(t_i - t_{i-1})(t_i \times C_i + t_{i-1} \times C_{i-1})}{2} + \frac{t \times C_t}{Kel} + \frac{C_t}{(Kel)^2}$ $MRT_{0-\infty} = \frac{AUMC_{0-\infty}}{AUC_{0-\infty}}$
V_z/F	L	$V_z/F = CL/F \times \frac{1}{Kel}$
V_{ss}/F	L	$V_{ss}/F = MRT \times CL/F$
Number of Kel points	—	will be determined using number of points used in computing Kel. If Kel cannot be estimated, zero.
Lower Limit of Kel	h	will be determined using lower limit on time to be included in the calculation of Kel
Upper Limit of Kel	h	will be determined using upper limit on time to be included in the calculation of Kel
Ae	mg	urine concentration \times urine volume
Ae%	%	Ae / Dose
CLr	L/h	$CLr = \frac{Ae}{AUC_{0-\infty}}$

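### SAP Appendix 1 divides a urinary amount collected to 24 or 48 h by AUC to infinity, so CLr is biased low, and it writes Ae% without the factor 100 (minor priority)

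*SAP*

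**What the plan says.** Protocol 10.1 leaves the calculation of each PK parameter to the SAP, so SAP Appendix 1 is where these formulas are fixed.

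- **Urinary amounts.** The SAP's List of PK Parameters defines two: Ae0-24, "Cumulative urinary excretion amount of drug from zero to 24 hour", and Ae0-48, "Cumulative urinary excretion amount of drug from zero to 48 hour". No amount extrapolated to infinity is defined. In Appendix 1, Ae carries no time index.
- **CLr.** Appendix 1 sets CLr = Ae/AUC0-inf. SAP 2.2.2 lists CLr for unchanged edaravone only.
- **End of collection.** Protocol 9.2.4.2 and SAP 7.2 set forced voids at 24 h and 48 h, with an exception for the last one: "Forced micturition at 46 h post-dose for subjects dosed 4 h after meals". In the study as reported this means condition C, because SAP 9.2 shows the fifth condition to be 2 hours after a low-fat meal.
- **More than one time point.** SAP 7.1.3.2 allows geometric statistics only when "all the individual Ae, Ae% and CLr is greater than 0 in each sampling time point".
- **Ae%.** The SAP list calls it "Urinary excretion ratio of drug", and Appendix 1 gives Ae/Dose with unit %. The protocol's list of PK abbreviations has "Cumulative percentage of drug excreted in urine".

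**The concern.** Renal clearance is an amount excreted over an interval divided by the plasma AUC over that same interval. Here the numerator stops when collection stops, while the denominator is extrapolated to infinity. The quotient is then not CLr but CLr multiplied by the fraction of exposure already past. That fraction depends on the collection time and on the terminal half-life, so a difference in elimination profile between meal conditions could appear as a small difference in renal clearance.

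The SAP also leaves open which Ae enters. The wording in SAP 7.1.3.2 suggests urinary parameters at more than one time, which makes a 24 h CLr a live reading, and that is where the bias is largest.

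Ae% raises a separate point of notation: a quantity with unit % whose formula gives a fraction. CLr, Ae and Ae% are all listed endpoints summarised by treatment, so their formulas should give what their names say.

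**Working it through.** The plan states no numerical value for CLr or Ae%, so there is no figure to reproduce. The check is of formulas against definitions, followed by the size of the discrepancy.

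**Inputs**
- CLr = Ae/AUC0-inf, and Ae% = Ae/Dose in % (SAP Appendix 1).
- T = 24, 46 or 48 h (SAP 7.2, Protocol 9.2.4.2).
- Terminal half-life of the suspension: 5.1 to 11.8 h, fasted, from the first phase I study (Protocol section 1, clinical study results).
- Dose 105 mg (Protocol 8.3).
- Assumption: f, the share of AUC0-inf carried by the terminal exponential, is 0.05 to 0.30. The documents do not give f. Setting f = 1, so that all exposure declines at the terminal rate, gives an upper bound.

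**CLr.** If renal clearance is constant, Ae(0-T) = CLr x AUC(0-T). The SAP formula then returns

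CLr x AUC(0-T)/AUC0-inf, with shortfall 1 - AUC(0-T)/AUC0-inf = f x 2^(-T/t1/2).

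T is the end of urine collection. It is not the t of the SAP's AUC0-t, which is the last quantifiable plasma time.

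| t1/2 (h) | T (h) | f = 0.05 | f = 0.30 | f = 1 (bound) |
|---|---|---|---|---|
| 5.1 | 24 | 0.19% | 1.15% | 3.83% |
| 5.1 | 46 | 0.01% | 0.06% | 0.19% |
| 5.1 | 48 | 0.01% | 0.04% | 0.15% |
| 11.8 | 24 | 1.22% | 7.33% | 24.42% |
| 11.8 | 46 | 0.34% | 2.01% | 6.71% |
| 11.8 | 48 | 0.30% | 1.79% | 5.96% |

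**46 h against 48 h.** At the nominal times, with t1/2 = 11.8 h, the C-to-fasted ratio of CLr is distorted by a factor (1 - 0.0671)/(1 - 0.0596) = 0.992 at the bound, and (1 - 0.0201)/(1 - 0.0179) = 0.998 at f = 0.30. Both are under 1%.

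**After matching intervals.** Ae(0-T)/AUC(0-T) = CLr, so the truncation bias is zero when CLr is constant.

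**Ae%.** As an illustration of scale, take 1.05 mg excreted. As written, 1.05/105 = 0.010. With the factor, 0.010 x 100 = 1.0%. The SAP does write x 100 for AUC%ex in the same appendix, and for CV% and geometric CV% in SAP 6.1.

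**The case against.** The best defence is that Ae without an index naturally means all the urine collected. On that reading the shortfall is at most about 2% under the assumed f. The 7.3% figure needs Ae0-24, the longest half-life and the largest assumed share together, and the half-life range comes from an earlier study over 30 to 300 mg. This is a fair limit on the size. It does not make the formula right, and it does not settle which Ae is used.

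Three stronger readings are tempting, and the documents do not support them.

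- **A reader might infer that condition C's urinary results are not comparable with the others.** The 46 h void is disclosed in both documents, and at the nominal times its effect on the ratio is under 1%. It is a labelling matter.
- **A reader might infer that Ae% will be reported 100 times too small.** The unit column says %, and the protocol defines a percentage. Appendix 1 also leaves out other scaling: CL/F and CLr are in L/h from mg and ng·h/mL, which needs a factor of 1000 that is not shown. A misprint is unlikely. What stands is that the SAP writes x 100 for its other percentages and not for this one.
- **A reader might infer a gap because CLr is missing from the parameters not calculated when Kel is missing.** Without AUC0-inf the quotient cannot be formed anyway, so no result changes.

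It is also true that SAP 8.4.2 models only Cmax and the AUCs, and that SAP section 1 gives the SAP precedence. Under the SAP, CLr, Ae and Ae% are listed and summarised only (SAP 8.4.1).

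**Conclusion.** The point stands, at minor priority. As written, CLr is a truncated amount over an extrapolated AUC. It is biased low by about 0.2 to 7.3% if Ae0-24 is used, and by at most about 2% if the 48 h amount (46 h in condition C) is used. The bounds with all exposure declining at the terminal rate are 24% and 6 to 7%. These sizes rest on constant renal clearance, the 5.1 to 11.8 h half-life range, and a terminal-phase share that is assumed.

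The Ae% formula is wrong if taken literally, but the intended quantity is clear. A reader should not infer any effect on the primary food-effect analysis: none of these urinary parameters enters it.

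**What to change.** In SAP Appendix 1, and in the List of PK Parameters where it applies:

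1. Compute CLr from Ae and AUC over the same interval and state the interval. The simplest choice is CLr = Ae0-24/AUC0-24. AUC0-24 is already a listed parameter, every condition has a forced void at 24 h, and no Kel is needed, so CLr would also survive a profile with no estimable terminal slope. The match holds to within the sampling windows in SAP 7.2 (30 min for the void, 15 min for the blood sample).
2. Write Ae% = Ae/Dose x 100, and define it as the cumulative percentage of the dose, in line with the protocol.
3. Label condition C's last cumulative amount Ae0-46.

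The cost is a few lines of SAP wording and the matching lines of code, with no new data. The downside is that urine collected after 24 h no longer contributes to CLr, although it still contributes to the cumulative Ae and Ae%. If the sponsor prefers to keep the second day, an AUC to the actual end of collection (48 h, or 46 h in C) would be equally sound.
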